5.6 Statistical Analysis

- What statistical test will be done?
- Provide sample size determination and analysis (include anticipated rate of screen failures, study discontinuations, lost to follow-up etc.).
- Describe how, where and by whom the data will be analyzed.

For each measure (i.e., reflexive latency, intrinsic stiffness, reflexive force, passive stiffness, and stress relaxation from Aim 1, along with the spinal load, SL , from Aim 2), we will run a univariate analysis of variance to verify potential differences between study groups (i.e., independent factor: participant group with five levels). A significant ANOVA will be followed with post-hoc pairwise comparison using Bonferroni's procedures. Prior to these analyses, parametric assumptions will be evaluated. As needed, data transformations will be used, or a non-parametric approach will be employed.

The statistical analyses will be led by the PI will be overseen by [name]

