In this application, forces and deformations experienced in spinal tissues are referred to as spinal loads, and are the result of the active and passive mechanical responses of lower back tissues (i.e., internal forces) to the physical demand of an activity (i.e., external forces), in order to assure spinal equilibrium and stability.³³⁻³⁵ When performing a physical activity, active (motor or sensory) responses of lower back tissues to the activity demand determine the trunk and pelvic motions. The resultant trunk and pelvic motions in turn determine lumbar posture and passive tissue contribution (due to deformation) to spine equilibrium and stability. Therefore, alterations in active and passive aspects of lower back MB, along with changes in the way a physical activity is performed, alter spine equilibrium and stability, and thus ultimately the spinal loads.

There is a large body of literature, including some from our laboratory, concerning the differences in the way a physical activity is performed between individuals with healthy backs, and those with acute/sub-acute/chronic or experimentally-induced LBP.³⁶⁻⁴¹ Despite some discrepancies, that are likely driven by the heterogeneity of population with non-specific LBP, abnormalities like larger pelvic contribution to trunk motion, more in-phase and less variable lumbo-pelvic coordination during trunk forward bending and backward return, have been widely reported in patients with non-specific LBP.³⁶⁻⁴¹ A large contribution of pelvis to trunk motion during forward bending has been suggested to be associated with higher spinal loads.⁴² It has been further shown that abnormalities in trunk and pelvic motions, observed in patients with non-specific LBP, linger beyond pain alleviation.⁴³⁻⁴⁵ Consistently, similar abnormalities in trunk

and pelvic motions have been reported in individuals with a history of LBP.^{46, 47} Individuals with LBP also demonstrate abnormalities in trunk and pelvic motions during activities of daily living like walking^{48, 49} and sit-to-stand.^{50, 51} Moreover, correlations between psychological factors and differences in trunk and pelvic motions among LBP patients have also been reported.^{45, 52} In this project, we will investigate whether these differences in the way a physical activity is performed in veterans with *different LBP experiences* are associated with potential differences in spinal loads (i.e., Aim 2).

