The specific objective of this study is to generate evidence in support of the feasibility of our developed methods for the evaluation of 1) relative contribution of lower back tissues to spinal loads, and 2) the resultant spinal loads experienced during daily activities **in veterans with non-specific LBP**. Results of this feasibility study will enable proper design of our future projects, wherein we will investigate the role of spinal loads experienced in daily life activities in clinical presentation of LBP. We have developed several innovative computational and experimental methods for a comprehensive and personalized assessment of spinal loads. Specifically, the relative mechanical contribution of active and passive lower back tissues to spinal loads is assessed using advanced measures of [bulk] lower back mechanical behavior (MB), whereas muscular responses to physical demands of daily activities and the resultant spinal loads are evaluated using our finite element model of human spine. We have used the methods proposed in this application extensively for evaluation of [bulk] lower back MB and spinal loads in asymptomatic individuals. This project will demonstrate the sensitivity of our measures for capturing abnormalities in lower back MB and spinal loads in patients with non-specific LBP by completing the following two aims to achieve our objective [*given the feasibility nature of this project and lack of adequate power, no specific hypothesis has been provided*]:

Aim-1: Feasibility of distinguishing potential differences in lower back MB between veterans with different LBP experiences. We will characterize lower back MB in three gender-balanced groups of veterans between 20 and 70 years old. These will include veterans with 1) *chronic LBP and a Roland-Morris Disability Questionnaire (RMDQ) score of >12 (n=18)*, 2) *chronic LBP and RMDQ score of ≤12 (n=18)*, 3) *no recent history of LBP and currently asymptomatic (n=18, serving as control group)*. Participants will be recruited from the population served by the Lexington, KY, VA Medical Center. We will determine passive stiffness of the lower back and its relaxation along with its active intrinsic and reflexive mechanical properties, using our sudden perturbation and stress-relaxations tests. Given the reported differences in trunk neuromuscular behavior and lumbo-pelvic coordination, we expect to see differences in our measures between patient groups targeted for this project.

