5.0 Study Procedures

5.1 Study Design

- **Study Design:** Describe experimental design of the study. Include sequential and/or parallel phases of the study, including durations, and explain which interventions are standard of care and which procedures are being done for research purposes.

This is a cross-sectional, observational study to investigate differences in **1**) active and passive aspects of lower back MB and **2**) spinal loads experienced during simulated daily activities between three veteran groups. Each participants will complete one data collection session during which they will complete a number of experiments and surveys.

- **Risk vs Benefit:** Include a description of how anticipated risk will be minimized and include an analysis of risk vs. potential benefit.

The potential risks of this study will be outlined in the informed consent document, and discussed with participants during the screening meeting. While the risk associated with the tasks performed during biomechanical assessment is no more than the risk experienced during daily life, some participants may experience muscle and/or joint soreness associated with the tests that are self-limiting and last a few minutes to a few hours. Mild discomfort may also occur during EMG preparation consisting of mild skin rubbing (with alcohol), possible shaving (with electric clippers), and the removal of adhesive tape holding the electrodes after test completion. The PI have run similar experiments with well over 100 healthy participants and 30 patients with LBP without any adverse incidents. Also, no injuries have been reported from similar measurements in the literature. Participants may feel unpleasant or uncomfortable answering some questions on the self-reported questionnaires. We will ensure participants that their answers are confidential and also inform them that they may choose not to answer any question.

Data security protections: To protect confidentiality, data on paper will be kept in locked filing cabinets and will be identifiable only by unique study ID numbers. Identifying participant information will be kept separate from other study-related materials.

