Sample size justification: The purpose of this SPiRE project is to generate the required data for effect size calculation of future merit grants. In the absence of preliminary data from veterans with LBP, we calculated a sample size using effect sizes estimated from our earlier investigations of back-healthy individuals as well as reports of relevant measures in the literature. Based on our earlier studies of asymptomatic individuals,^{56, 57, 66} a sample size of 10 would have a power of >80% for detection of significant (p = 0.05) differences in the proposed measures of lower back MB following acute exposure to awkward working posture. Further, using results in the literature,⁶⁷⁻⁶⁹ a sample size (i.e., sum of two groups) of 18 was estimated to detect reported significant effect sizes between individuals with and without LBP with 80% power. Therefore, a sample size of 18 for each group is selected to facilitate sample size calculation and power analyses for our future merit grant applications while maximizing our chances of discovering potential differences in lower back MB and spinal loads between groups.

- **Vulnerable Populations:** As applicable, provide information on any added protections for vulnerable populations.

Not Applicable

- **Data and Specimen Banking:** If applicable include information on data and specimen banking.

Not Applicable

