5.2 Recruitment Methods

- State how many subjects will be needed.
- Describe when, where, how and by whom potential subjects will be identified and recruited.
- Describe materials that will be used to recruit subjects, e.g., advertisements. Include materials as an appendix or separate attachment.

- Describe any payments to subjects, including the amount, timing (at the end of the study or pro-rated for partial study participation), method (e.g., cash, check, gift card), and whether subjects will experience a delay in receiving the payment.

We will recruit 54 gender-balanced veterans in the following three groups: 1) with chronic, non-specific LBP and a Roland-Morris Disability Questionnaire (RMDQ) score of >12 (n=18), 2) with chronic, non-specific LBP and a RMDQ score of ≤12 (n=18), 3) asymptomatic and no a recent history of non-specific LBP (n=18; serving as control group)

Participants will primarily be recruited from veteran populations receiving treatments at the Lexington VA Medical Center in Lexington, KY. This center has two facilities and several community-based clinics in the surrounding areas, and serves a population of more than 92,000 veterans. Veteran population in our local communities who do not receive care at the Lexington VA Medical Center will also be recruited. [name] (Co-I) from the Department of Physical Medicine and Rehabilitation, with assistance from [name] (Clinical Research Assistant), will lead our patient recruitment efforts.

Recruitment will be done between months 6 and 18 of the project period. During this period, PI and Co-I will meet providers that see patients with LBP to seek their assistance in identification of patients with LBP. This will include, but not limited to, primary care physicians, physical therapist, chiropractors, acupuncturists, and etc., to inform them about the study and target patient population. These providers will be asked to inform their potentially eligible patients about our study and give them our IRB approved recruitment flyer. In addition to posting flyers in these clinics, we will have one of our research staff to be present in select days to provide more information to the interested patients. We will also distribute our study flyers to local institutions that serve Veterans. The distribution of study flyers will also include the use of listservs that will be sent to Veterans who are studying at the University of Kentucky.

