5.4 Inclusion/Exclusion Criteria

- Describe the criteria that determine who will be included in or excluded from the study.

Inclusion/Exclusion Criteria			
	Group-1	Group-2	Group-3
Current condition	Non-specific LBP	Non-specific LBP	Asymptomatic
LBP Experience	Chronic*	Chronic*	No recent history
RMDQ score	>12	≤12	N/A
Pain severity (0-9)	≥2	≥2	N/A
Inclusion criteria	
 • Age between 21 and 70 years old • Body mass index between 18 and 32 		
Exclusion criteria	
 • Any spinal surgery [e.g., spinal fusion surgery] • Any abnormalities in lower extremity joints due to disease or injury that would likely affects lower back mechanics [e.g., lower limb amputation or peripheral arterial disease] • Any safety concern [e.g., pregnancy] • Any medical condition for which we can't determine the impact of our experimental procedures. [e.g., we don't know whether our measurement instrument will affect pacemakers.] • Inability to read or verbally comprehend English • Unwilling or unable to comply with study protocol • Retention of legal advice or an open / pending legal case related to 		

	LBP

 • Definition recommended by the NIH task force on research standards for chronic LBP will be used: a pain in the lower back on more than half of days over the past 6 months. 	

Eligibility of participants will be determined in a two-step screening procedure involving an initial brief screening followed by an on-site screening. The brief screening will be done over phone for participants who contact the study personnel via information given in the flyer or it will be done in the clinic by the research staff who will be present in clinic for participant recruitment. During the brief screening an overview of study objectives and procedures will be provided, and the following provisional eligibility criteria will be verified:

- Age between 21 and 70 years
- Body mass index between 18 and 32, calculated using self-report of weight and height
- Current, a recent history, or no recent history of LBP
- Any spinal surgery [e.g., *spinal fusion surgery*]
- Any abnormalities in lower extremity joints due to disease or injury that would likely affects lower back mechanics [e.g., *lower limb amputation or peripheral arterial disease*]
- Any safety concern [e.g., *pregnancy*]

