5.5 Study Evaluations

- **Describe all evaluations to be conducted (including screening; tests/questionnaires that will be administered; any procedures that subjects will be required to complete) and data collection methods. Include materials as an appendix or separate attachment.**

In each data collection session, participants will first be instrumented with sensors to enable measurement of kinematics and muscle activity, similar to procedures we used in our earlier studies.⁷⁰⁻⁷³ Specifically, wireless inertial measurement units (Xsens MTW, Xsens Technologies, Enschede, Netherlands)⁷⁴ will be used to measure rotations of the thorax and pelvis, and surface EMG electrodes will be used to measure the activity of erector spinae, rectus abdominus, internal and external obliques. Participants will then be asked to stand on a force plate and perform a forward bending and backward return test.^{38, 72, 75} Participants will be instructed to bend from an upright standing posture to their maximum comfortable forward bending posture and then return to the upright posture at a self-selected pace. Participants will then be instructed to perform the following activities of daily life at a self-selected pace: walking on level^{76, 77} surfaces, sit-to-stand and stand-to-sit motions,⁷⁹ and lowering and lifting a 10 lb load to their knee height.⁸⁰ These activities have been selected because they represent basic

but repetitive activities of daily life, and we have successfully used them in our earlier investigation of spinal loads among asymptomatic non-veterans, as well as persons with unilateral lower limb amputation. Finally, sudden perturbation followed by stress-relaxation tests will be conducted as in earlier studies and as explained below. Each of the above tests will take less than 5 minutes, and we will provide break periods between each set of tests to minimize fatigue and discomfort.

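### The three observational groups are balanced on gender only and the planned ANOVA has no age term, so a systematic age gap could enter the group differences meant to supply effect sizes for future grants.

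*Combined protocol and SAP*

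**What the plan says.** Section 5.1 describes the design: "This is a cross-sectional, observational study to investigate differences in" lower back mechanical behaviour and spinal loads between three veteran groups. Gender is the only balancing factor. Section 3.0 (Aim 1) refers to "three gender-balanced groups of veterans between 20 and 70 years old", and Section 5.2 says "We will recruit 54 gender-balanced veterans in the following three groups". Age appears only as an eligibility window, given in Section 5.4 as "Age between 21 and 70 years old"; the lower limit is 20 in Section 3.0.

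For each of six measures (five for Aim 1, plus the spinal load summary SL for Aim 2), Section 5.6 says "we will run a univariate analysis of variance to verify potential differences between study groups". Participant group is the only factor, and a significant result is followed by Bonferroni pairwise comparisons. No covariate is named.

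The sample size justification in Section 5.1 gives the purpose of the study: to "generate the required data for effect size calculation of future merit grants".

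**The concern.** Nothing in an observational comparison makes the groups alike in age. A shared eligibility window of 49 years limits a gap but does not balance it. Recruitment (Section 5.2) runs through clinicians who treat LBP and also through mailing lists of veterans studying at a university. That makes an age gap plausible, but the plan does not tie either channel to a group.

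The plan's own references suggest that age matters:

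- Refs 71, 73 and 70, cited in Section 5.5 for reflex latency, intrinsic stiffness and the passive response, are titled on age effects.
- Refs 72 and 75 are also titled on age. They are cited where participants "perform a forward bending and backward return test".
- Section 2.0 connects that movement to the Aim 2 outcome: "A large contribution of pelvis to trunk motion during forward bending has been suggested to be associated with higher spinal loads".

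An age gap would then put an age component into the group differences, and a later grant would treat that component as an effect of LBP status. Recalculating the next sample size from the same estimate cannot remove it. A gap in the opposite direction would hide a real difference.

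**Working it through.** The plan states no figure for age, so there is none to reproduce, and its sample size is not in dispute here.

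**From the documents:** 18 per group, three groups, N = 54, significance level 0.05.

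**Assumed, not in the documents:** age SD 14 years (a uniform spread over 21 to 70 gives 49/√12 = 14.1); both LBP groups shifted by the same amount from controls; within-group correlation *r* between age and the measure of 0.3 to 0.5, with weaker values shown as well.

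**Model.** The measure has within-group SD 1, and *g* = gap/14 is the age gap in SD units.

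- Spurious LBP-control difference = *r* × *g*.
- With no true effect the group means are (*rg*, *rg*, 0). The noncentrality is 18 × (2/3) × (*rg*)² = 12(*rg*)², and the false rejection rate comes from the noncentral F(2, 51).
- Sampling standard error of a pairwise difference = √(2/18) = 0.33 SD.
- Unadjusted RMSE = √(2/18 + (*rg*)²). The table gives RMSE from simulation, 40,000 runs per cell.

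Example: for a 10-year gap and *r* = 0.5, *rg* = 0.5 × 10/14 = 0.357, the noncentrality is 12 × 0.1276 = 1.53, and the rejection rate is 17.3%.

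| Gap (years) | *r* | Spurious difference (SD) | False rejection, group only | RMSE, group only | RMSE, age added |
|---|---|---|---|---|---|
| 5 | 0.3 | 0.11 | 6.0% | 0.350 | 0.324 |
| 5 | 0.4 | 0.14 | 6.8% | 0.361 | 0.312 |
| 5 | 0.5 | 0.18 | 7.8% | 0.379 | 0.295 |
| 10 | 0.3 | 0.21 | 9.1% | 0.399 | 0.336 |
| 10 | 0.4 | 0.29 | 12.6% | 0.438 | 0.322 |
| 10 | 0.5 | 0.36 | 17.3% | 0.487 | 0.303 |

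At *r* = 0.1 to 0.2, a 5-year gap gives 0.04 to 0.07 SD and 5.1 to 5.4%; a 10-year gap gives 0.07 to 0.14 SD and 5.4 to 6.8%. With no systematic gap the ANOVA keeps its 5%.

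**With age in the model**, simulated false rejection was 4.9 to 5.1% in all 12 cells (gaps of 0, 5 and 10 years; *r* of 0, 0.3, 0.4 and 0.5), and the spurious difference was about 0. If age is unrelated to the measure, adjustment raises RMSE slightly: from 0.33 to 0.34 with no gap or a 5-year gap, and to 0.35 with a 10-year gap.

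**Chance gaps.** The standard error of a difference in mean age is 14 × √(2/18) = 4.67 years. Without any systematic gap, a given pair of groups would differ by more than 5 years 28% of the time.

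**Effect on a later grant.** With age SD 12, a 10-year gap and *r* = 0.3, the spurious part is 0.3 × 10/12 = 0.25 SD. A true difference of 0.5 SD is then read as 0.75. By n = 2(1.96 + 0.84)²/d², the planned size falls from 63 to 28 per group.

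**The case against.** - **The size is assumed.** The evidence on age consists of reference titles, which give neither size nor sign, and no age gap is stated. This stands. At *r* = 0.1 to 0.2 the bias is small and adjustment is close to neutral for total error.
- **Support is uneven across measures.** For maximum reflexive force, Section 5.5 cites ref 57, which is titled on prolonged trunk flexion; the nearest age title is ref 71, on reflexive behaviour in general. For SL the link runs through forward bending and an association that Section 2.0 calls only suggested. This stands, and it is a reason to show adjusted and unadjusted results together.
- **Only some contrasts are affected in the calculation.** With both LBP groups shifted equally, the comparison of high and low disability has no modelled bias. It would have some only if those two groups differed in age.
- **This is a feasibility study.** Sections 3.0 and 5.8 state no specific hypothesis, and 3.0 also disclaims adequate power, so the false rejection rate matters less than usual. The effect sizes are still what the study is meant to produce.
- **Age could be examined later.** It could, since it is asked at screening, but a covariate chosen after seeing the data is weaker than one named in advance.

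**Conclusion.** The concern holds as a minor point. In the supplied text nothing guards against age confounding; whether it occurs depends on an age gap and a correlation that the documents do not give. Under the assumptions above, the spurious LBP-control difference is 0.11 to 0.18 SD for a 5-year gap and 0.21 to 0.36 SD for a 10-year gap, and less if age is weakly related to the measures. Against a standard error of 0.33 SD the estimates are imprecise either way. For correlations of 0.3 to 0.5, adjustment lowers total error in every case with a gap; if age is irrelevant, the loss is slight.

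**What to change.** In Section 5.6, prespecify for each of the six measures an ANCOVA with group and age. Give the group factor three levels to match the groups recruited; the section now says five.

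- Report age-adjusted differences with 95% confidence intervals beside the unadjusted ANOVA. Let the ANCOVA decide whether pairwise tests follow, and apply Bonferroni to the adjusted comparisons.
- Base effect sizes for future grants on the adjusted differences, divided by the unadjusted within-group SD. Dividing by the ANCOVA residual SD would inflate them by 1/√(1 − *r*²), which is 5 to 15% for *r* of 0.3 to 0.5.
- For SL, show the unadjusted difference with equal prominence, because the load actually experienced is the Aim 2 quantity.
- State the age-adjusted counterpart of the non-parametric fallback.
- Tabulate age and body mass by group. Keep any body-mass adjustment, including for SL, as a sensitivity analysis.

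The cost is a short addition to the analysis section and one of 51 error degrees of freedom. Age is already asked at screening and no participants are added. For assumed true means of 0.8, 0.4 and 0 SD, unadjusted power with no gap is 54%. If age is unrelated to the measure, ANCOVA power is 53%, 52% and 50% for gaps of 0, 5 and 10 years. If the correlation is 0.3 to 0.5, it is 57 to 66%, 57 to 65% and 54 to 63%.

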LBP is a significant health problem and is strongly associated with opioid use among veterans.³⁻⁶ Despite decades of intensive research efforts, LBP persistence, recurrence, and transition from the acute to chronic stage is not managed effectively for majority of patients.¹⁴⁻¹⁷ This clinical challenge arises, in part, because of the inability to determine the etiology of symptom (i.e., patients with non-specific LBP). The objective of this feasibility project is to verify the sensitivity of our biomechanical outcome measures for capturing potential differences in lower back mechanics between veterans with different LBP experiences. Successful completion of this project will warrant conduct of larger projects (i.e., using merit grant mechanism) to verify the role of lower back biomechanical abnormalities in LBP presentation. Given technological advances that have made biomechanical assessment more accessible, screening patients with non-specific LBP for biomechanical abnormalities can help reduce the possibility of symptom persistence and relapse due to excessive force and deformation experienced in spinal tissues. Improvement in clinical outcomes of treatment for non-specific LBP will diminish

reliance on opioids for the symptom management of particularly veterans with chronic LBP.

- **Patient Population:** Provide description of the study population (delineate all categories of subjects – patients, providers, family members, employees, etc.). Include anticipated enrollment numbers. How many participants.samples per group studies? Justify the sample size to obtain power for statistical analysis.

We will conduct a cross-sectional study involving three groups of research participants with and without LBP:

Group-1: Veterans with chronic, non-specific LBP and a Roland-Morris Disability Questionnaire (RMDQ) score of >12 (gender-balanced, n1=18)

Group-2: Veterans with chronic, non-specific LBP and a RMDQ score of ≤12 (gender-balanced, n2=18)]

Group-3: Asymptomatic veterans with no recent history of LBP (gender-balanced, n3=18)

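### Gender is balanced in every group but left out of the ANOVA, so if men and women differ on a measure the group tests are conservative and lose some power

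*Combined protocol and SAP*

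**What the plan says.** Gender balance is a repeated design commitment. Section 3.0 (Aim 1) states "We will characterize lower back MB in three gender-balanced groups of veterans". Section 5.1 attaches it to each group, for example "Asymptomatic veterans with no recent history of LBP (gender-balanced, n3=18". Section 5.2 repeats it for the whole sample: "We will recruit 54 gender-balanced veterans in the following three groups". Age and body mass index, by contrast, are only restricted to a range in section 5.4.

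Section 5.6 covers six measures: reflex latency, intrinsic stiffness, reflexive force, passive stiffness, stress relaxation and spinal load. For each, "we will run a univariate analysis of variance to verify potential differences between study groups", and the model is described by "independent factor: participant group with five levels". (Five levels conflicts with three groups; that is a separate error in the same sentence.) The follow-up is also by group alone: "A significant ANOVA will be followed with post-hoc pairwise comparison using Bonferroni's procedures". Transformation or a non-parametric approach is allowed if assumptions fail. The text reviewed does not enter gender as a factor, covariate or stratum anywhere.

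**The concern.** A factor used to build the design normally belongs in the model. When it is balanced across groups and then omitted, it does not move the group differences, but its sum of squares goes into the residual. The test then judges the group differences against an error variance larger than the one that actually governs them.

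Two things are at stake. First, power: section 3.0 concedes that it is inadequate, while section 5.1 wants the best chance of finding differences. Second, the SD passed on: section 5.1 says the purpose is to supply data for effect sizes in later grants, and the one-way residual SD would contain any gender difference without saying so.

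**Working it through.** **Inputs from the documents.** Three groups of 18, gender-balanced (sections 3.0, 5.1, 5.2); one-way ANOVA on group (5.6); significance level 0.05 (5.1).

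**Assumptions.** Balance means 9 men and 9 women per group. Men and women differ by D within-gender SD, equally in every group. The documents give no value for D, so 0 to 1.5 is shown. For power, both low back pain groups are shifted by 1 SD from controls.

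**The plan's own figure.** Section 5.1 quotes a total of 18 for two groups at 80% power but gives no effect size or SD, so it can only be inverted: 9 against 9, two-sided 0.05, implies a standardised difference of about 1.41. It says nothing about gender.

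**Error variance.** With 9/9 balance, gender is orthogonal to group. The gender sum of squares has noncentrality 54 × D²/4. In the one-way model it is pooled with the other 50 error degrees of freedom, so the expected residual mean square, in within-gender variance units, is

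1 + (54 × D²/4)/51 = 1 + 18(D/2)²/17.

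At D = 1 this is 1 + 4.5/17 = 1.26, and the SD is √1.26 = 1.12.

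**Size and power.** The one-way test is F(2, 51) with gender in the error; the adjusted test is F(2, 50). For group shifts (1, 1, 0) the mean is 2/3, the squared deviations sum to 1/9 + 1/9 + 4/9 = 2/3, and the noncentrality is 18 × 2/3 = 12. Adjusted power is 86% at every D. The one-way results below were simulated from these chi-square distributions.

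| D | Residual variance | Residual SD | True size of 5% test | Power, one-way | Power, group + gender |
|---|---|---|---|---|---|
| 0 | 1.00 | 1.00 | 5.0% | 86% | 86% |
| 0.25 | 1.02 | 1.01 | 4.8% | 86% | 86% |
| 0.5 | 1.07 | 1.03 | 4.1% | 84% | 86% |
| 1.0 | 1.26 | 1.12 | 2.4% | 78% | 86% |
| 1.5 | 1.60 | 1.26 | 0.9% | 67% | 86% |

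Simulation error affects only the last digit (about 0.1 point in size, 1 point in power). A rank-based fallback on group alone (Kruskal-Wallis) behaves the same way: size about 2.5% at D = 1 and 1.0% at D = 1.5.

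**What balancing already delivers.** The true SD of a two-group mean difference is √(2/18) = 0.333 at every D. Had gender been left to chance it would be √[(2/18)(1 + D²/4)] = 0.344, 0.373 and 0.417 at D = 0.5, 1.0 and 1.5.

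**If balance fails.** With 6 women in one group and 9 in another, a 1 SD gender difference shifts the contrast by (9/18 − 6/18) × 1 = 0.17 SD, half of its 0.333 standard error. Over the three groups, 6/9/9 women leaves the one-way test still below 5% (about 4%), because the inflated error outweighs the bias. With 3/9/9 the shift is 0.33 SD and the false-positive rate rises to about 10%.

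**The case against.** The strongest reply is that the loss is conditional and may be negligible. The documents report no gender difference for any measure. At D = 0 nothing is lost, at 0.25 under one point of power, at 0.5 about two. Only at about 1 SD or more is the loss material. That stands, and the point is worded accordingly. Section 5.5 states no scaling of stiffness, force or spinal load to body size, so a real gender difference is plausible, but it is not documented.

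Several stronger readings are tempting, and the documents do not support them:

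- *The balance is wasted.* It is not. Balancing gives unconfounded group contrasts and a smaller true standard error. What is lost is recognition of that precision in the estimated error.
- *Confidence intervals will be too wide.* Section 5.6 plans an F test and pairwise comparisons and specifies no intervals.
- *Effect sizes for later grants will be wrong.* At D = 1 an effect standardised by the one-way SD is about 11% smaller (1/1.12 = 0.89). But a total SD suits a later mixed-gender study analysed without gender, and the within-gender SD suits one that adjusts for it. The documents do not say which is intended.
- *The groups will end up unbalanced.* Section 5.2 describes no quota or rule to secure the balance, but nothing predicts failure. Imbalance is a contingency that adjustment covers.

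The feasibility status also counts. Sections 3.0 and 5.8 disclaim a formal hypothesis, and under the planned balance the error is towards too few positive findings.

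**Conclusion.** The point holds in conditional form. Every group is gender-balanced by design and the planned model ignores gender. If the genders differ on a measure, the F test and pairwise comparisons are conservative: at an assumed 1 SD difference, size is about 2.4% instead of 5% and power about 78% instead of 86%. At 0.25 SD or less there is practically no loss. These figures rest on exact 9/9 balance, a common gender difference in all groups, and the assumed 1 SD shift in both low back pain groups. Group contrasts are not biased while the balance holds.

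Severity is modest. A reader might infer that the planned analysis is invalid; it is not. It leaves possible precision unused, and it would lose its protection against gender bias if recruitment fell well short of balance.

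**What to change.** In section 5.6:

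- Replace the one-way ANOVA with a linear model containing group (three levels) and gender (two levels) for all six measures, and take the Bonferroni pairwise comparisons from that model.
- Make any non-parametric fallback account for gender too, for example by a gender-stratified rank test.
- Report gender-adjusted group means with both the within-gender residual SD and the total SD, so that later grants can use the one that matches their own analysis.
- Show group-by-gender means descriptively. With 9 per cell, a common group effect in both genders can be checked only weakly.

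The cost is a short rewrite of a sentence that needs correcting anyway for its number of levels, one error degree of freedom (51 to 50), and no new data. If gender turns out not to matter, power is practically unchanged at 86%.
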